##### Secondary Objectives

##### Phase II:

The secondary objectives of the Phase II portion of the trial are to define the safety & tolerability, progression free survival, duration of response, and overall survival of TAK228 in patients with relapsed lymphoma.

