During the first cycle of TAK228, the following laboratory studies should be performed on day 15 (within 3 business days) - CBC with differential, Serum chemistries - Na, K, Cl, CO2, BUN, Cr, Ca, Mg, phosphorus, total protein, albumin, alkaline phosphatase, AST, ALT, total bilirubin, uric acid, and LDH, and a fasting serum glucose, triglycerides, cholesterol panel. Fasting is defined as nothing to eat for at

least 4-6 hours before blood draw.

Hemoglobin A1c should be obtained prior to cycle 1 day 1, cycle 3 day 1, cycle 6 day 1, cycle 9 days 1 and cycle 12 day 1.

An electrocardiogram will be obtained pre-dose (within 28 business days) prior to start of cycle 1 and within 3 days of starting each subsequent cycle.

The following staging studies should be performed at completion of 2 cycles of TAK228 (within 5 business days prior to starting cycle 3) – CT scans of neck, chest, abdomen, and pelvis; Chest X-ray – PA and lateral; and unilateral bone marrow biopsy and unilateral aspirate if bone marrow is involved with lymphoma at baseline. An optional PET/CT scan may be obtained at completion of 2 cycles of TAK228 at the discretion of the treating physician.

The following staging studies should be performed at completion of every 2 cycles beyond the first 2 cycles of TAK228 (i.e., +/- 5 business days prior to starting cycle 5, 7, 9, and 11): CT scans of neck, chest, abdomen, and pelvis; Chest X-ray – PA and lateral; and optional unilateral bone marrow biopsy and unilateral aspirate if bone marrow is involved with lymphoma at baseline at the discretion of the treating physician; An optional PET/CT scan may be obtained at completion of every 2 cycles of TAK228 at the discretion of the treating physician, but should be considered if previously FDG avid lymph nodes remain enlarged on CT imaging or physical examination.

In consenting patients, for correlative studies, a 10 ml of blood sample [1 heparin containing green top tube and 1 purple top tube (5 ml/tube)] will be collected at each of the following time points: cycle 1 day 1 (2-4 hours after dose), and cycle 2 day 1 (2-4 hours after dose). These samples will be transported within 4 hours (+/- 2 hours) of collection to the RPPA Core Laboratory Facility and/or Lymphoma Tissue Bank, depending on time of collection, at M. D. Anderson Cancer Center (MDACC). Blood from green top tubes will be processed for isolation of peripheral blood mononuclear cells (PBMC) using standard laboratory protocols.

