#### **Evaluation At Completion of Study**

Patients will be evaluated by the treating physician and a relevant history and physical examination, including performance status evaluation and vital signs, will be recorded 1 week (+/- 7 business days) after completion of TAK228. Toxicities will be graded according to the NCI CTC v4.0 during this visit.

The following laboratory studies should be performed 1 week (+/- 7 business days) after completion of TAK228 – CBC with differential, Serum chemistries - Na, K, Cl, Glucose, CO2, BUN, Cr, Ca, Mg, phosphorus, total protein, albumin, alkaline phosphatase, AST, ALT, total bilirubin, PT/PTT/INR, urinalysis, uric acid, LDH, and quantitative immunoglobulins, and a fasting serum glucose, triglycerides, and cholesterol panel. In addition, an EKG should be performed 1 week (+/- 7 business days) after completion of TAK228. Fasting is defined as nothing to eat for at least 4-6 hours before blood draw.

The following staging studies should be performed 2 weeks (+/- 14 business days) after completion of TAK228 – CT scans of neck, chest, abdomen, and pelvis; Chest X-ray – PA and lateral; and optional bilateral bone marrow biopsy and unilateral aspirate if bone marrow is involved with lymphoma at baseline at the discretion of the treating physician. An optional PET/CT may be performed 2 weeks (+/- 14 working/business days) after completion of TAK228 at the discretion of the treating physician.

For correlative studies, 10 ml of blood sample [2 heparin containing green top tubes (5ml/tube)] will be collected when a patient is taken off study (+/- 14 business days). These samples will be transported within 6 hours of collection to the RPPA Core Laboratory Facility and/or Lymphoma Tissue Bank, depending on time of collection, at M. D. Anderson Cancer Center (MDACC). Blood from green top tubes will be processed for isolation of peripheral blood mononuclear cells (PBMC) using standard laboratory protocols.

Patients will be evaluated by the treating physician and a relevant history and physical examination, including performance status evaluation and vital signs, will be recorded 1 week (+/- 7 business days) after completion of TAK228. Toxicities will be graded according to the NCI CTC v4.0 during this visit.

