Patients will be monitored by a cohort size of 5 after the first 15 patients according to the following stopping boundaries for OR at two cycles and reason for dose modification at one cycle. If the number of responses required for moving the trial to next stage has not been achieved, the patient enrollment will be halted until enough responses observed.

For cohorts I), TAK228 will be considered promising if it yields an OR rate of 45% at two cycles and a REASON FOR DOSE MODIFICATION rate of 25% at one cycle. A sample size of 25 ensures that, if the cohort is not terminated early, a posterior 90% credibility interval for overall response rate will have width of 0.310 at most, under the assumption of a 45% of OR rate. The prior probabilities of OR and REASON FOR DOSE MODIFICATION for the experimental regimen are modeled by beta distributions ( $Beta(0.9,1.1)$  and  $Beta(0.5,1.5)$ , respectively). Denoting probabilities of OR rate and REASON FOR DOSE MODIFICATION rate by ( $p_{OR}$ ,  $p_{Reason\ for\ dose\ modification}$ ), the following decision criteria will be applied: Stop the trial if  $Prob(p_{OR} < 45\% \mid data) > 0.95$  or  $Prob(p_{Reason\ for\ dose\ modification} > 25\% \mid data) > 0.95$ .

Patients will be monitored by a cohort size of 5 after the first 15 patients according to the following stopping boundaries for OR at two cycles and REASON FOR DOSE MODIFICATION at one cycle. If the number of responses required for moving the trial to next stage has not been achieved, the patient enrollment will be halted until enough responses observed.

Patients who are treated on study and have at least 1 disease restaging study prior to termination of study participation will not be replaced with an additional patient added to their disease cohort. Patients who are treated on study and fail to have at least 1 disease restaging study prior to termination of study participation will be replaced with an additional patient added to their disease cohort at the discretion of the principle investigator.

The duration of the study as a whole is defined first patient to start the screening period to the last patient to conclude their therapeutic period. The anticipated accrual is 3 patients per month on this trial. Thus, accrual for the study is expected to be complete in approximately two years. The total duration of the study is anticipated to be approximately three years.

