### Efficacy Analysis

Summary statistics will be provided for continuous variables. Frequency tables will be used to summarize categorical variables. Logistic regression will be utilized to assess the effect of patient prognostic factors on the response rate and the toxicity rate. The distribution of time-to-event endpoints, such as overall survival, progression free survival, and response duration, will be estimated using the method of Kaplan and Meier. Comparison of time-to-event endpoints by important subgroups will be made using the log-rank test. Cox proportional hazard regression may be employed for multivariate analysis on time-to-event outcomes.

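### No disease assessment is scheduled after the end-of-treatment scan, so PFS and duration of response lose events in patients who stop TAK228 without progression

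*Combined protocol and SAP*

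**What the plan says.** The secondary objectives include "progression free survival, duration of response, and overall survival of TAK228 in patients with relapsed lymphoma". The Efficacy Analysis section says that time-to-event endpoints "such as overall survival, progression free survival, and response duration, will be estimated using the method of Kaplan and Meier". Neither that section nor the Analysis Plan defines PFS or response duration or gives a censoring rule, and the Analysis Plan names time to progression where the Efficacy Analysis names PFS.

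The section on evaluation during study places the first restaging "within 5 business days prior to starting cycle 3". It continues: "The following staging studies should be performed at completion of every 2 cycles beyond the first 2 cycles of TAK228", with cycles 5, 7, 9 and 11 given as the time points. The section on evaluation at completion of study then adds one more staging: "The following staging studies should be performed 2 weeks (+/- 14 business days) after completion of TAK228". The same instruction is repeated further down that section. No later imaging, visit or contact for progression is scheduled.

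The Phase II design section defines the length of the study as running from the "first patient to start the screening period to the last patient to conclude their therapeutic period".

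**The concern.** Disease status is followed for as long as the patient takes TAK228, not until progression. A patient who stops for toxicity, by choice, or at the end of planned treatment, and who has not progressed at the end-of-treatment scan, has no later scheduled assessment from which progression could be dated. Unless stopping is itself counted as an event, which the plan does not say, a Kaplan-Meier analysis has to censor that patient at about that scan.

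Two things are at stake. First, events are lost in cohorts of at most 25. Second, Kaplan-Meier treats censored patients as having the same later risk as those still under observation. If patients who stop have a worse prognosis, or if risk rises once the drug is withdrawn, the curves are too high. Durability matters here because the rationale faults mTORC1 inhibition for benefit that does not last, and because the trial is meant to pick lymphoma subtypes for further study. Knowing who is alive would not close this gap, since vital status does not date progression.

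**Working it through.** **Stated duration.** Inputs from the plan: 75 patients at most, 3 per month, 28-day cycles. Accrual is 75/3 = 25 months. No maximum number of cycles is stated. The latest cycle named is in the haemoglobin A1c schedule ("cycle 9 days 1 and cycle 12 day 1"), so 12 cycles is a working assumption: 12 × 28 = 336 days = 11.0 months. The total is 25 + 11.0 = 36.0 months, which matches the stated three years (34.2 or 35.1 months with 10 or 11 cycles). On this reading the timeline has no room for follow-up of the last patients after treatment.

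**Window of the last scan.** Fourteen business days are 18–20 calendar days. The scan can therefore fall from 4–6 days before the last dose (14 − 18, 14 − 20) to 32–34 days after it (14 + 18, 14 + 20).

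**Longest observable response duration.** For a responder first documented at day 56 who stops without progression after k cycles, the longest duration is 28k + 14 − 56 days, shifted by up to 20 days either way by the window:

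- k = 4: 70 days
- k = 6: 126 days
- k = 8: 182 days
- k = 12: 294 days, or 294/30.44 = 9.7 months. With the scan at day 34 after the last dose it is 314/30.44 = 10.3 months.

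The first restaging may itself fall up to 5 business days before cycle 3, which adds about a week at most.

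**Lost events and bias in PFS.** The plan gives no PFS or stopping rates, so these inputs are assumptions: overall median PFS of 6 months; exponential times; half the patients with 1, 2 or 3 times the rate of both progression and non-progression stopping; 20% or 40% stopping before month 11; censoring at stop + 0.5 month, or at month 11.5; 400,000 simulated patients. The stopping share can mean stops actually observed before progression, or the latent chance of stopping before month 11 whether or not progression comes first. Both are shown. Event shares cover rate ratios 1–3, and bias covers ratios 2–3.

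| Stopping without progression | Patients with a PFS event | Events of 25 | Kaplan-Meier bias at 6–11 months |
|---|---|---|---|
| None | 70–74% | about 18 | none |
| 20%, observed | 60–64% | 15–16 | +0.4 to 1.8 points |
| 40%, observed | 49–53% | 12–13 | +1 to 4.2 points |
| 20%, latent | 65–68% | 16–17 | +0.2 to 0.9 points |
| 40%, latent | 59–62% | about 15 | +0.4 to 2 points |

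At rate ratio 1 (no link) the bias is nil in every row.

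**Scale of the noise.** With 25 patients and no early censoring, the standard error is √(0.50 × 0.50/25) = 0.10 at 6 months and √(0.29 × 0.71/25) = 0.09 at 11 months, that is 9–10 points.

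**A second route to bias.** Let risk change after the drug is stopped, with a median time to non-progression stop of 12 or 6 months and treatment capped at 12 cycles. If the off-drug hazard is 2–3 times the on-drug hazard, the Kaplan-Meier median is too long by 0.5–1.0 month when on-drug median PFS is 6 months, and by 1.5–3.3 months when it is 12. If the hazard is unchanged, a 6-month median is estimated without bias and a 12-month median is not reached.

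**The case against.** A reader might infer more than the documents support, and four such readings should be set aside.

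- **Measurement ends on the day TAK228 stops.** It does not. A full staging follows, possibly as late as 34 days after the last dose, and would catch early progression off drug.
- **The plan censors at treatment stop.** It states no rule. Censoring at about the last scan is what Kaplan-Meier would do in practice, but that is an inference.
- **Response duration is capped for everyone by treatment length.** Responders who progress on drug are fully observed. The limit binds only for those who leave without progression, and the 10-month figure rests on the assumed 12 cycles. If treatment continues to progression, the limit concerns early leavers only.
- **PFS and response duration are biased upward as a matter of course.** Ending at a fixed last cycle is administrative censoring. A censored duration enters as a lower bound, and the result is a median not reached, not a wrong one. Bias needs a link between stopping and prognosis, or a change in risk off drug. Even the largest figure above, 4.2 points, is under half a standard error.

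It can also be said that these endpoints have no target, comparator or decision rule, and that the text available is in abstract form, so follow-up detail might lie elsewhere. The first point stands and limits the weight of the finding. The second lowers confidence somewhat, but nothing in the text points to such a section, and the definition of study duration agrees with there being none.

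**Conclusion.** The point holds as a cheap improvement to two secondary endpoints. The primary endpoint and both stopping rules are unaffected, since they rest on response and dose modification.

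Followed as written, the plan loses progression dates after the end-of-treatment scan. The loss of information does not depend on any link between stopping and risk, but its size rests on the assumed 6-month median PFS and the assumed stopping shares: from about 18 events to about 13 of 25 in the heaviest case shown. For response duration, a patient who stops without progression after 4 cycles contributes about 70 days at most. Bias is possible but conditional, and it is modest beside the sampling error of a 25-patient cohort.

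**What to change.** 1. In the section on evaluation at completion of study, add that for patients without progression at the end-of-treatment staging, the dates of progression, next anti-lymphoma therapy and death are recorded from routine imaging and records available to the centre, up to a stated data cut-off. Extend the definition of study duration in the Phase II design section to that cut-off; otherwise the two sections would conflict.
2. In the Efficacy Analysis section, define PFS as time to progression or death from any cause, and response duration as first CR or PR to progression or death. Use the added dates. State that the main analysis censors at the last disease assessment before next therapy. Tabulate the reason for each censoring. Bring the Analysis Plan's time to progression into line with PFS.
3. Add one sensitivity analysis that counts a stop for toxicity, clinical decline or new therapy as an event.
4. If follow-up is not extended, label both endpoints as on-treatment estimates.

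The cost is some chart abstraction and one extra analysis, with no study scans added. Routine scans are irregularly timed, so late progression dates will be less exact. Capture will also be incomplete for patients who go elsewhere for care: the Study Enrollment section shows that patients are enrolled at one centre, not that they are followed there afterwards.

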#### **Study Enrollment:**

The study population for this research will consist of participants from:

Only at MDACC

**Estimated Accrual:**

Total Accrual at MDACC: Phase II: Maximum 75, Minimum 45  
Estimated monthly accrual at MDACC: 3

**Screening Accrual:**

Does this study include a screening component? No

**Accrual Comments:**

This is an open label, phase II clinical trial to evaluate the safety and efficacy of TAK228 in patients with relapsed lymphoma. The maximum sample size is 75 and the minimum samples size is 24 for Phase II.

**Is this an NCI-Cancer Therapy Evaluation Protocol (CTEP)?** No

**Is this an NCI-Division of Cancer Prevention Protocol (DCP)?** No

**Statistical Considerations:**

This is an open label, phase II clinical trial to evaluate the safety and efficacy of TAK228 in patients with relapsed lymphoma. The maximum numbers of patients that will be recruited are 75 for the phase II.

The primary objective of trial is to determine the best overall response rate, defined as the combination of complete (CR) and partial (PR) response rates in patients with relapsed lymphoma when treated with TAK228. The secondary objectives are to define the safety & tolerability, overall survival, progression free survival, duration of response, determination of response associated clinical characteristics, of TAK228 in patients with relapsed lymphoma.

The overall response assessment at 2 cycles will be utilized to determine if additional accrual in each phase II cohort is warranted, but will not be the primary endpoint.

**Phase II cohort definitions and expectations**

Differences in the natural history of the lymphoma subtypes allowed on this clinical trial will require stratification. Therefore, we will separate accrued patients into three independent cohorts. As this is the first detailed evaluation of TAK228 in relapsed lymphoma, we will employ a bayesian trial design to avoid potential futility and/or toxicity.

**Cohort A**

Cohort A will be defined as aggressive lymphoma (diffuse large b cell lymphoma, follicular grade 3b, transformed lymphomas, and mantle cell lymphoma). Clinical experience with mTORC1 inhibitors in relapsed aggressive lymphoma is variable, but is most commonly reported to be 28-38% ORR.(17) It is assumed that TAK228 will have a target overall response rate at 2 cycles of 35% for this patient cohort. A response rate of 10% or lower is considered a failure and the new regimen will be rejected under this circumstance.

### **Cohort I**

Cohort I will be defined as indolent lymphoma (follicular lymphoma grade 1 – 3a, small lymphocytic lymphoma, and marginal zone lymphoma). Clinical experience with mTORC1 inhibitors in relapsed indolent lymphoma is variable, but is most commonly reported to be 11-54% ORR.(17) It is assumed that the new regimen will have a target overall response rate at 2 cycles of 45%. A response rate of 20% or lower is considered a failure and the new regimen will be rejected under this circumstance.

### **Cohort H**

Cohort H will be defined as Hodgkin lymphoma. Clinical experience with mTORC1 inhibitors in relapsed Hodgkin lymphoma is variable, but small studies have identified ORR as high as 42%, though larger studies have not yet confirmed these results.(17) It is assumed that the new regimen will have a target overall response rate at 2 cycles of 35% for this patient cohort. A response rate of 10% or lower is considered a failure and the new regimen will be rejected under this circumstance.

### **Phase II design:**

During the phase II study, patients will be treated with TAK228 at the MTD established in the sponsored trials. Three independent cohorts of patients will be enrolled: 1) patients with aggressive lymphoma (diffuse large B cell lymphoma, follicular grade 3b, transformed lymphomas, and mantle cell lymphoma); 2) patients with indolent lymphoma (follicular lymphoma grade 1 – 3a, small lymphocytic lymphoma, and marginal zone lymphoma); and 3) patients with Hodgkin lymphoma. We will run the three cohorts as three parallel trials. The maximum number of patients needed for each cohort is 25.

For each of the patient cohort, the overall response (OR) at two cycles and dose modifications required based upon toxicity (referred to below as reason for dose modification) at one cycle will be monitored. Simultaneously using Bayesian stopping boundaries calculated based on Beta-Binomial distributions. Independence was assumed between OR and Reason for dose modification.

For each of the patient cohort, the overall response (OR) at two cycles and dose modifications required based upon toxicity (referred to below as reason for dose modification) at one cycle will be monitored. Simultaneously using Bayesian stopping boundaries calculated based on Beta-Binomial distributions. Independence was assumed between OR and reason for dose modification.

For cohorts A) and H), TAK228 will be considered promising if it yields an OR rate of 35% at two cycles and a reason for dose modification rate of 30% at one cycle. A sample size of 25 in each patient cohort ensures that, if the cohort is not terminated early, a posterior 90% credibility interval for overall response rate will have width of 0.297 at most, under the assumption of a 35% of OR rate. The prior probabilities of OR and reason for dose modification for the experimental regimen are modeled by beta distributions (*Beta*(0.7,1.3) and *Beta*(0.6,1.4), respectively). Denoting probabilities of OR rate and reason for dose modification rate by (pOR , pReason for dose modification) Confidential, the following decision criteria will be applied: Stop the trial if  $\text{Prob}(pOR < 35\% | \text{data}) > 0.95$  or  $\text{Prob}(p\text{Reason for dose modification} > 30\% | \text{data}) > 0.95$ .

Patients will be monitored by a cohort size of 5 after the first 15 patients according to the following stopping boundaries for OR at two cycles and reason for dose modification at one cycle. If the number of responses required for moving the trial to next stage has not been achieved, the patient enrollment will be halted until enough responses observed.

For cohorts I), TAK228 will be considered promising if it yields an OR rate of 45% at two cycles and a REASON FOR DOSE MODIFICATION rate of 25% at one cycle. A sample size of 25 ensures that, if the cohort is not terminated early, a posterior 90% credibility interval for overall response rate will have width of 0.310 at most, under the assumption of a 45% of OR rate. The prior probabilities of OR and REASON FOR DOSE MODIFICATION for the experimental regimen are modeled by beta distributions ( $Beta(0.9,1.1)$  and  $Beta(0.5,1.5)$ , respectively). Denoting probabilities of OR rate and REASON FOR DOSE MODIFICATION rate by ( $p_{OR}$ ,  $p_{Reason\ for\ dose\ modification}$ ), the following decision criteria will be applied: Stop the trial if  $Prob(p_{OR} < 45\% \mid data) > 0.95$  or  $Prob(p_{Reason\ for\ dose\ modification} > 25\% \mid data) > 0.95$ .

Patients will be monitored by a cohort size of 5 after the first 15 patients according to the following stopping boundaries for OR at two cycles and REASON FOR DOSE MODIFICATION at one cycle. If the number of responses required for moving the trial to next stage has not been achieved, the patient enrollment will be halted until enough responses observed.

Patients who are treated on study and have at least 1 disease restaging study prior to termination of study participation will not be replaced with an additional patient added to their disease cohort. Patients who are treated on study and fail to have at least 1 disease restaging study prior to termination of study participation will be replaced with an additional patient added to their disease cohort at the discretion of the principle investigator.

The duration of the study as a whole is defined first patient to start the screening period to the last patient to conclude their therapeutic period. The anticipated accrual is 3 patients per month on this trial. Thus, accrual for the study is expected to be complete in approximately two years. The total duration of the study is anticipated to be approximately three years.

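### The one-cycle toxicity stopping rule counts toxicity-driven dose modifications without saying whether a toxic death or a permanent stop in cycle 1 is an event

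*Combined protocol and SAP*

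**What the plan says.** The section on cohort definitions and expectations gives the purpose of the design: "we will employ a bayesian trial design to avoid potential futility and/or toxicity". The Phase II design section then names the monitored toxicity variable: "dose modifications required based upon toxicity (referred to below as reason for dose modification) at one cycle will be monitored".

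For cohorts A and H the drug is promising at "a reason for dose modification rate of 30% at one cycle". For cohort I the figure is "a REASON FOR DOSE MODIFICATION rate of 25% at one cycle". A cohort stops for toxicity when the posterior probability that this rate exceeds 30% (A and H) or 25% (I) is above 0.95. On looks, the plan says: "Patients will be monitored by a cohort size of 5 after the first 15 patients".

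No section of the supplied text defines dose modification or says whether permanent discontinuation or death due to toxicity counts as one.

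The Population for Analysis and Protocol Monitoring sections add a study-wide hold if drug-related toxicity is judged unacceptable. That hold has no event definition and no numeric limit. The reviews scheduled alongside it follow 5, 10, 15, 20 and 25 patients who have finished all their treatment.

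**The concern.** The rule exists to close a cohort that is too toxic, and the posterior probability can use only the events that are counted. Suppose a patient's first serious toxicity in cycle 1 is fatal. No dose has been modified, so on the literal wording that patient enters as a non-event and lowers the estimated toxicity rate. A patient taken off drug permanently at the first toxicity is in the same position unless stopping is treated as a form of modification.

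This is a question about the numerator. It arises even if every dosed patient stays in the denominator. What is at stake is whether the boundary responds to early toxic deaths and stops, and whether two people applying the same text to the same patients would reach the same decision.

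**Working it through.** **Inputs, all from the Phase II design section.** Toxicity priors: Beta(0.6, 1.4) for A and H, Beta(0.5, 1.5) for I. Response priors: Beta(0.7, 1.3) and Beta(0.9, 1.1). Thresholds: 30% and 25%. Cut-off: 0.95. Looks: 15 and 20 patients, with a maximum of 25 per cohort.

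**Step 1: reproduce the plan's own figures.** The plan states 90% credible-interval widths for response at n = 25 of 0.297 (A and H) and 0.310 (I). The equal-tailed interval is taken from Beta(a + np, b + n(1 − p)).
- A and H: Beta(0.7 + 8.75, 1.3 + 16.25) = Beta(9.45, 17.55); width 0.2966.
- I: Beta(0.9 + 11.25, 1.1 + 13.75) = Beta(12.15, 14.85); width 0.3099.

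Both match, so the beta-binomial model is being read as intended.

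**Step 2: toxicity boundaries.** For threshold t, find the smallest x for which P(p > t) > 0.95 under Beta(a + x, b + n − x).

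| Cohort | n | One event below the boundary | At the boundary |
|---|---|---|---|
| A, H | 15 | 7 events: 0.893 | 8 events: 0.960 |
| A, H | 20 | 9 events: 0.906 | 10 events: 0.961 |
| I | 15 | 6 events: 0.874 | 7 events: 0.952 |
| I | 20 | 8 events: 0.913 | 9 events: 0.965 |

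The boundary tables that the section announces are not in the text available, so these values are derived from the stated priors and cut-offs.

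**Step 3: can the event definition change a decision?** Take 15 patients, of whom two died of toxicity or stopped for good because of it with no earlier modification.
- A and H, 6 modifications plus these 2. As worded: Beta(6.6, 10.4), posterior 0.766, continue. All counted: Beta(8.6, 8.4), posterior 0.960, stop.
- I, 5 modifications plus these 2. As worded: Beta(5.5, 11.5), posterior 0.729, continue. All counted: Beta(7.5, 9.5), posterior 0.952, stop.

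**Step 4: effect on the chance of stopping by 20 patients.** With boundaries c15 and c20,

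P(stop) = P(X15 ≥ c15) + Σ over x < c15 of P(X15 = x) · P(X5 ≥ c20 − x),

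where X15 and X5 are binomial counts in the first 15 and the next 5 patients. The counted rate is set at the threshold, and 2 or 5 percentage points of uncounted toxic stops or deaths are added. Those points are an assumption.

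| Cohort | Rate entering the rule | Stop at 15 + stop at 20 | By 20 |
|---|---|---|---|
| A, H, as worded | 30% | 0.0500 + 0.0183 | 0.068 |
| A, H, 2 points added | 32% | 0.0711 + 0.0265 | 0.098 |
| A, H, 5 points added | 35% | 0.1132 + 0.0424 | 0.156 |
| I, as worded | 25% | 0.0566 + 0.0123 | 0.069 |
| I, 2 points added | 27% | 0.0817 + 0.0185 | 0.100 |
| I, 5 points added | 30% | 0.1311 + 0.0309 | 0.162 |

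**The case against.** The strongest reply is that dose modification is undefined rather than narrowly defined. The text does not say that holds and reductions count, nor that stopping does not. Permanently stopping a drug for toxicity can ordinarily be read as a modification that toxicity required. The variable is also labelled as the reason for modification, which could point to the toxicity itself and not to the change in dosing; on that reading even a fatal toxicity might count. This stands in part. A reader might infer that the plan deliberately excludes discontinuations, or that a death falls outside the rule on every reading, and the text supports neither. What it does show is that a rule with a 0.95 cut-off rests on a term that can be read in two ways, and that the literal reading leaves out an unpreceded toxic death.

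The second reply is that other safeguards exist. The study-wide hold could act on a cluster of deaths or stops, and nothing in its wording confines it to the scheduled reviews. Patients are assessed on days 8, 15 and 22 of cycle 1, and everyone dosed enters the safety analysis. All of this is true, so it would be wrong to conclude that such cases have no consequence. None of it repairs the count, however: the hold has no threshold, and no text carries it or the safety analysis into the Bayesian boundary.

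The third reply is that the effect may be small, since many patients who stop or die will have had a modification first and are already counted. That also stands, which is why the illustration uses 2 to 5 points. It rules out the claim that the worse a toxicity is, the less likely it is to be counted.

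**Conclusion.** The point holds as a gap in the definition of the monitored event. On the literal wording, a toxic death in cycle 1 without a prior modification is not counted, and permanent discontinuation for toxicity is counted only on a broad reading that the text does not state. Two such patients are enough to turn a stop into a continue at the 15-patient look in any cohort.

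Under the assumed 2 to 5 uncounted points, the chance of a toxicity stop by 20 patients would rise from 0.068 to between 0.098 and 0.156 in A and H, and from 0.069 to between 0.100 and 0.162 in I, if those cases counted. These figures assume that the counted rate sits at the threshold, that all dosed patients stay in the denominator, and that looks fall at 15 and 20.

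A reader might go further and assume 15 uncounted points, which gives 0.068 against 0.456 in A and H. The documents offer no rate that would justify that scenario, so it should not be taken as the size of the problem. The definition is still worth correcting because the rule is the plan's only numeric protection against toxicity and the correction is short.

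**What to change.** In the Phase II design section, state once that the monitored toxicity event is any dose modification, permanent discontinuation of TAK228 or death, due to toxicity, that occurs during cycle 1. Use that event in both decision criteria: the one for cohorts A and H and the one for cohort I. Priors, thresholds, looks and the one-cycle window stay as they are. Tie the event to its occurrence during cycle 1, because wording based on onset could bring in later modifications and so change the window.

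The cost is one sentence, plus attribution of cycle-1 stops and deaths to toxicity or to another cause. The text schedules toxicity grading at the cycle-1 visits but does not say that the reason for stopping is recorded, so that should be confirmed. The counted rate will be the same or higher, so a cohort with early toxic stops or deaths is more likely to reach the boundary. Keeping 30% and 25% means holding the broader event to the same limits, which the sponsor should confirm is intended. No treatment rule changes; only what is counted.
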